Cover Page

02/16/2022

GME Study

Gene Expression, Meditative Movement, and Emotional Distress (GME)

NCT04213872

Study Protocol and Statistical Analysis Plan

2. Method

This was a single-group pilot study testing the effects of 8 weeks of MM practice on changes in cognitive function, anxiety, sleep quality, depression, and selected gene expression factors. The enrollment goal was to consent and assign forty BCSs to an eight-week MM program. Measures on cognitive functioning, associated symptoms/conditions, and gene expression data were collected before and after the 8-week MM program. This study utilized the Paired Sample t-test of SPSS [22] to report p-values from the analysis of pre- and post-MM intervention changes in the cognitive functioning, associated symptoms/conditions, and gene expression data. This study was approved by both the IRB committees at Pomona Valley Hospital Medical Center (PVHMC as the primary IRB) and at Arizona State University (ASU as the secondary IRB).

2.1 Study Population

2.1.1 Eligibility Criteria

Inclusion criteria: minimum 45 years of age; female patients diagnosed with breast cancer, stages 0–III; between six months and five years past primary treatment; ability to speak or understand English; and post-menopausal for at least one year. Exclusion criteria: Women who were unable to stand (e.g., wheelchair or walker bound); patients who were too weak or ill; patients on antibiotics; women working on night shift; and patients with anemia or uncontrolled diabetes. Pregnant women, mentally disabled persons, and prisoners were excluded.

2.1.2 Participant Recruitment

On a daily basis, the clinical trials research coordinator (CRC) at the Pomona Valley Hospital Medical Center (PVHMC) Cancer Care Center (CCC) in Pomona, CA, identified potential participants with the support of site oncologists, site oncology nurses, and the site cancer registry. Flyers were displayed at the Breast Cancer Care Center at the CCC and other affiliated breast cancer care centers in the region. The site cancer registry prepared a mailing list based on the eligibility criteria and invitations were mailed. The CRC generated a list of potential participants based on referrals from the CCC staff and from phone calls from potential participants responding to flyers and mailings.

2.1.3 Screening and Consenting

There were two options for screening and consenting potential participants. In the first option, the site PI or the CRC contacted potential participants referred by the oncology team to screen for study interest and eligibility. In the second option, potential participants responded to the mailed invitation sent by the CRC. Study eligibility and enrollment for participants recruited and screened through both options were confirmed upon review of their medical records after obtaining written consent from potential participants in accordance with Good Clinical Practice (GCP) and Health Insurance Portability and Accountability Act of 1996 (HIPAA). As CCC staff members, the CRC and site PI had access to medical records. After reception of signed Informed Consent form and medical chart review, study participants were scheduled to attend the MM classes.

2.2 Study Intervention

2.2.1 The Intervention

The MM (Qigong/Tai Chi Easy) intervention is a standardized, protocol [23] with a formal training program for practice leaders from the Institute of Integral Qigong and Tai Chi (IIQTC) and has been used in previous research with various populations [8, 24, 25]. This practice is similar to the short, simplified forms used in the majority of Tai Chi research protocols showing health benefits [26]. The protocol is taught as a series of repeated and simple-to-learn movements rather than long chains of choreographed moves that are more difficult to learn (typical of how traditional long-form Tai Chi is taught).

In this study, the MM intervention was implemented over 8 weeks with class sessions once a week at the Pomona Cancer Care Center. Each class session was approximately one hour. The participants learned gentle

movements, ranging from mild to moderate levels of exertion. The participants were asked to practice the MM exercises at home, at their own pace, most days of the week, totaling at a minimum, 2 ½ to 3 hours per week and to log their MM practices in a logbook provided to them. A professionally produced DVD and manual demonstrating a core set of 10, and additional exercises for variety were given to participants to help guide their practice at home. The lead investigator, a certified Mind-Body Medicine Practitioner, and certified QG/TCE practice leader assisted the research participants with the MM sessions. The PI and CRC provided support and guidance to the participants during the MM program.

2.3 Measures

Basic demographic data (gender, ethnicity/race, and age) was collected at baseline. Self-report data on cognitive abilities (perceived and objective assessments), anxiety, depression, and sleep quality, and blood draws to examine gene expression, were collected pre- and post- 8-week MM program (within two weeks prior to and subsequent to the intervention).

2.3.1 Cognitive Function (CF) and Cognitive performance (CP) Tests

Cognitive function was assessed using both a self-report and an objective performance test.

Self-reported CF was assessed using the Functional Assessment of Cancer Therapy-Cognitive Function (FACT-COG), 37 items, validated, including 4 subscales including perceived cognitive impairment (PCI), perceptions of effects of cognitive function on quality of life (QOL), and perceived cognitive abilities (PCA) and comments from other (OTH [27-29]

CP Tests: Two brief measures of attention/working memory from the Wechsler Adult Intelligence Scale (WAIS-III) Third Edition [30, 31] were used to assess CP: Digit Span and Letter-Number Sequencing, with reliability ratings of .90 and .82 respectively.

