2.4.2 Hypothesis Testing Data Analysis Plan

This study utilized the Paired Sample t-test of the SPSS statistical program to analyze the primary outcome changes in cognitive function anxiety, depression, and sleep quality over an 8-week period. Changes in BDNF, NF- κ B1, and TP53 gene expression results were analyzed using the paired sample t-test in SPSS to determine if the means of the pre- and post-MM gene expression data were significantly different.

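### The two WAIS-III tests are repeated in one uncontrolled group and tested against zero change, so any practice gain is counted in the change attributed to meditative movement

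*Combined protocol and SAP*

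**What the plan says.** Section 2 states the aim and the design together: "This was a single-group pilot study testing the effects of 8 weeks of MM practice". There is no comparison group.

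Section 2.3.1 gives cognitive function two components: "Cognitive function was assessed using both a self-report and an objective performance test". The performance component is "Digit Span and Letter-Number Sequencing, with reliability ratings of .90 and .82 respectively". The kind of reliability is not stated.

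Section 2.3 places both assessments "within two weeks prior to and subsequent to the intervention", so the two administrations are 8 to 12 weeks apart (8 weeks plus up to 2 on either side).

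Section 2.4.2 uses the paired t-test "to analyze the primary outcome changes in cognitive function anxiety, depression, and sleep quality over an 8-week period", and section 2 says that its purpose is "to report p-values from the analysis of pre- and post-MM intervention changes in the cognitive functioning".

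The documents mention no alternate test form, no retest norm or allowance, and no practice effect as a limitation.

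**The concern.** A paired t-test against zero answers whether the mean moved. It answers whether MM moved it only if scores would have stayed put without MM. For a performance test taken twice, earlier exposure may by itself raise the second score. With no control group, that gain is part of the mean change and nothing in the plan removes it.

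The stated reliabilities do not help. Reliability describes how well the women keep their rank order. A gain shared by all of them leaves the order intact and shifts the mean. If the reliabilities also hold as pre-post correlations, they make the SD of change small, so that a modest shared gain reaches significance more easily.

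These two tests are the only objective cognitive measures, cognitive function is listed first among the primary outcomes, and a practice gain pushes the result towards improvement. Section 2.4.1 describes pilots of this kind as a source of preliminary data for a clinical trial, so an inflated change could carry over into the planning of that trial.

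**Working it through.** The plan gives no figure for the practice gain, the SD of change or the significance level, so there is no stated result to reproduce. The calculation shows how the planned test behaves if a practice gain exists and MM has no effect.

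**Inputs from the documents**
- Pairs: 14 completers (2.4.1) less one missing post-program WAIS-III (2.4.3) = 13.
- Reliabilities: 0.90 for Digit Span and 0.82 for Letter-Number Sequencing (2.3.1).
- Planned completers: 40 × (1 − 0.20) = 32 (2.4.1).

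**Assumptions**
- Two-sided 5% level, so 2.5% in the direction of improvement.
- Pre-post correlation r equal to the stated reliability, or 0.70 as a weaker case.
- Normally distributed changes and equal SDs before and after.
- Practice gain g of 0.1 to 0.4 baseline SD.

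**Formulas, in baseline-SD units**
- SD of change = √(2(1 − r))
- Noncentrality = g × √n / SD of change, with n − 1 degrees of freedom
- Smallest significant mean change = half-width of the 95% interval = t(0.975, n − 1) × SD of change / √n

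**SD of change**
- r = 0.90: √0.20 = 0.447
- r = 0.82: √0.36 = 0.600
- r = 0.70: √0.60 = 0.775

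**Half-width at n = 13**, with t = 2.179 and √13 = 3.606
- r = 0.90: 2.179 × 0.447 / 3.606 = 0.27
- r = 0.82: 2.179 × 0.600 / 3.606 = 0.36
- r = 0.70: 2.179 × 0.775 / 3.606 = 0.47

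**Example of the noncentrality:** Digit Span, g = 0.2: 0.2 × 3.606 / 0.447 = 1.61. The chance that a noncentral t on 12 degrees of freedom exceeds 2.179 is then 31.7%.

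**Chance of a significant improvement with no MM effect, n = 13**

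| Practice gain (SD) | Digit Span, r = 0.90 | Letter-Number, r = 0.82 | Either test, r = 0.70 |
|---|---|---|---|
| 0 | 2.5% | 2.5% | 2.5% |
| 0.1 | 11.2% | 8.0% | 6.3% |
| 0.2 | 31.7% | 19.7% | 13.5% |
| 0.3 | 60.4% | 38.2% | 25.0% |
| 0.4 | 84.1% | 59.8% | 40.3% |

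The last column applies to each test taken singly. Simulation with 200,000 runs per case at gains of 0, 0.2 and 0.3 SD agrees for the first two columns (for example 31.8% and 60.4% for Digit Span).

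**More pairs do not help.** At the planned 32 completers, a gain of 0.2 SD gives 68.8% (r = 0.90), 44.7% (r = 0.82) and 29.3% (r = 0.70).

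**A control would help.** In a simulated comparison with a concurrent group that has the same practice gain (13 per group, an illustration), the false-improvement rate stays at 2.5% for gains of 0, 0.2 and 0.3 SD.

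**The case against.** **The practice gain is not in the documents.** This stands, and the percentages are therefore conditional. A reader might infer from them that a WAIS-III gain in this study is mostly practice, or probably a false positive. The documents do not support that, because nothing in them shows that a gain occurred or how large it was. With 13 pairs, a gain of 0.1 or 0.2 SD would more often than not fail to reach significance. What does not depend on the size is that any such gain is included whole in the estimated change.

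**The reliabilities may not be pre-post correlations.** This also stands. Their type is not given, and for the other scales the document quotes Cronbach's alpha (2.3.2, 2.3.3), which measures internal consistency. The higher figures rest on this assumption, and so does the argument that high reliability aggravates the problem. At a correlation of 0.70 the rates at 0.2 and 0.3 SD fall to 14% and 25%, still several times the nominal 2.5%.

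**It is a small pilot looking for trends (2.4.3).** This is fair as a description of its ambition. A reader might infer that the plan undertakes to announce a practice gain as better cognition, but it contains no such wording. It does say that it tests the effects of MM and reports p-values for primary outcomes, and it adds no caveat about retesting.

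**Every single-group study has this limit.** Largely true, and the design cannot now be changed. The point here is narrower: it applies to the two repeated performance tests, where the direction of a practice gain is known. FACT-COG is self-report and raises different questions.

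**Conclusion.** The point holds as a limit on what the WAIS-III analysis can show. The design and the zero null are confirmed by the documents: a paired t-test of change in one group cannot separate MM from practice on Digit Span or Letter-Number Sequencing.

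For an assumed practice gain of 0.2 to 0.3 SD, 13 pairs and a two-sided 5% level, the chance of a significant improvement without any MM effect is 32% to 60% for Digit Span and 20% to 38% for Letter-Number Sequencing if the stated reliabilities act as pre-post correlations. It is 14% to 25% if the correlation is 0.70. The gain, the correlation and the level are all assumptions. The presence of the bias, given any positive practice gain, depends on none of them.

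This is a low-cost improvement to analysis and reporting that changes what may be concluded from these two tests.

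**What to change.** In 2.4.2, for each WAIS-III test:

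1. Report the mean change with its 95% confidence interval, in raw and baseline-SD units, computed from the observed SD of change. This removes the need to assume a correlation.
2. State the lower limit as the largest practice gain the data exclude, that is, rule out as the sole explanation of the change. If the limit is at or below zero, say that no positive practice gain is excluded.
3. Describe the result as uncontrolled pre-post change that cannot be separated from practice, and do not report p<0.05 against zero as an MM effect on cognitive performance.

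No outside norm is needed. Three other remedies are best left out:
- A count of women beyond a reliable-change threshold is itself centred on zero. With a 0.3 SD gain and no MM effect, it would flag 9.9% (Digit Span) and 7.2% (Letter-Number) as improved instead of 2.5%.
- A pass/fail margin such as 0.3 SD has no basis in the documents and would be chosen after the participants had finished.
- A familiarisation run concerns a future study.

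The cost is a few sentences and a small re-analysis of existing data. The downside is that a WAIS-III gain becomes harder to claim.

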2.3.2 Profile of Mood States Short Form (POMS-SF)

The POMS-SF consists of 37 items, adjectives scored on a 5-point Likert scale [32]. The POMS is one of the most frequently used and validated scales in studies of psychosocial interventions with BCSs, and has been validated with Hispanics [33] and multicultural populations [34]. POMS consists of the Total Mood Disturbance (TMD) dimensions (tension-anxiety; depression-dejection; anger-hostility; confusion-bewilderment; Cronbach's alpha = .93). This pilot study reported results for the tension-anxiety and depression-dejection TMD dimensions (12 items).

2.3.3 Sleep Quality

The Pittsburgh Sleep Quality Index (PSQI): 19 items assess sleep, including subscales for subjective sleep quality, sleep latency, sleep duration, sleep disturbance, habitual sleep efficiency, daytime dysfunction and use of sleep medications [35]. A global PSQI score >5 distinguishes good from poor sleepers with 89.6 % sensitivity and 89.5% specificity and demonstrates Cronbach's $\alpha = 0.83$ [36].

2.3.4 Process Control, Manipulations and Fidelity

Each participant received a phone call or email midweek between class attendance (whether they attended or not) to remind them to document practice time (session/minutes) and weekly record level of exertion. MM Practice Logs were provided for participants to document home practice. The midweek contact served both as process control evaluation and as a method for encouraging adherence. Whenever a participant missed a scheduled class, she received an additional call to encourage adherence.

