2.4 Retention Strategies

The PI and CRC maintained contact with the study participants by telephone, in person, or email to encourage retention in the study. In addition, to providing log-book instructions and meeting time reminders during this contact, the CRC or PI encouraged questions and sharing on how they are experiencing the research study with goal of establishing a therapeutic alliance between the research staff and the study participants. The study participants were also encouraged to initiate contact with the PI or CRC with any questions or concerns by phone, email, or in person.

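### Section 2.4.3 treats the loss of participants as minor, but 13 of 27 consented women (48%) are absent from a completers-only analysis, and neither reasons nor the number of starters is reported

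*Combined protocol and SAP*

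**What the plan says.** **Loss and analysis set.** Section 2.4.1 sets a target of 40 with 20% attrition expected, then reports 27 consented and 14 completed. Section 2.4.3 limits all analyses to women who completed, does not impute unavailable post-intervention data, and expects no systematic bias on the ground that only a few women's data were lost. It gives one reason for missing data: schedule conflicts, for one participant's WAIS-III and logbook. Section 2.1.3 places chart review and confirmation of eligibility after written consent, and class scheduling after that.

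**Contacts during the programme.** Under Section 2.3.4, each woman is contacted by phone or email "to remind them to document practice time (session/minutes) and weekly record level of exertion". The purposes are stated: "The midweek contact served both as process control evaluation and as a method for encouraging adherence". For absence: "Whenever a participant missed a scheduled class, she received an additional call to encourage adherence". Section 2.4 describes contact by the PI and CRC, which may be the same contact. In addition "to providing log-book instructions and meeting time reminders during this contact", staff "encouraged questions and sharing on how they are experiencing the research study with goal of establishing a therapeutic alliance", and women were "encouraged to initiate contact with the PI or CRC with any questions or concerns by phone, email, or in person".

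**Where practice takes place.** Section 2.2.1 says that women were "asked to practice the MM exercises at home, at their own pace, most days of the week", for a weekly minimum of 2.5 to 3 hours. Of the weekly class it says: "Each class session was approximately one hour".

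**The concern.** A completers-only analysis describes the women who stayed. It carries over to all women who started only if those who left would have changed by about the same amount, or if very few left. Section 2.4.3 relies on the second condition. The counts in Section 2.4.1 do not support it on their face, and nothing reported allows a reader to test the first.

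Section 2.4.1 cites guidelines for pilots that gather preliminary data for a clinical trial. The size of the change, the expected attrition and the reasons for leaving are all inputs to that trial. If women left because they felt worse or saw no benefit, a completers' pre-post change would look too favourable. If they left because of distance, scheduling or ineligibility found on chart review, it need not.

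The contacts in Section 2.3.4 bear on the same gap. They are a natural place to learn why a woman missed a class or stopped, yet they are described only as serving process control and adherence.

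**Working it through.** **Inputs.** Consented 27, completed 14, target 40, expected attrition 20% (Section 2.4.1). Order of consent, chart review and class scheduling (Section 2.1.3). Analysis set and absence of imputation (Section 2.4.3). Class length and weekly practice minimum (Section 2.2.1). The number of women who began the programme, B, is not given. It lies between 14 and 27 if all 14 completers began.

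**1. The plan's own expectation.** 40 × (1 − 0.20) = 32 completers. At the same rate, 27 consented women would give 27 × 0.80 = 21.6 completers. The reported number is 14.

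**2. Loss from consent.** 27 − 14 = 13, and 13/27 = 48.1%. The exact (Clopper-Pearson) 95% interval is 28.7% to 68.1%. This is loss from all causes, counted from consent. It is not strictly comparable with 20% if the plan meant loss after starting.

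**3. Loss among starters.** The proportion is (B − 14)/B.

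| B | Lost before starting (27 − B) | Loss among starters |
|---|---|---|
| 14 | 13 | 0/14 = 0% |
| 17 | 10 | 3/17 = 17.6% |
| 18 | 9 | 4/18 = 22.2% |
| 20 | 7 | 6/20 = 30.0% |
| 27 | 0 | 13/27 = 48.1% |

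A loss of 20% or less requires B ≤ 14/0.80 = 17.5, so B ≤ 17. At least 27 − 17 = 10 of the 13 would have to have left before starting.

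**4. What this does to the estimate.** For any outcome:

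mean change in completers − mean change in all starters = [(B − 14)/B] × [mean change in completers − mean change in non-completing starters]

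The multiplier is 0 at B = 14, 0.30 at B = 20 and 0.48 at B = 27, against 0.20 at the planned attrition. At its largest it is 0.481/0.20 = 2.4 times the planned value. The second factor, the difference between completers and non-completing starters, cannot be estimated from anything reported. So neither the direction nor the size of any bias is known.

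**5. Reasons.** The one reason stated concerns a woman who missed the WAIS-III and did not return a logbook, and it reads as referring to a completer. Even if she were one of the 13, 13 − 1 = 12 would remain unexplained.

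**6. Home share of the weekly minimum (for the secondary point).** If the one-hour class counts towards the total: 1.5/2.5 = 60% to 2/3 = 67%. If it does not: 2.5/3.5 = 71% to 3/4 = 75%. The document does not say which applies. Either way, most of the minimum practice is out of the class leader's sight.

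**The case against.** **The sentence may be about missing items, or may be left over from planning.** It stands near the note on one woman's missing WAIS-III and logbook, and it is worded as an expectation. The ambiguity is real, but it does not rescue the text. The sentence comes directly after the completers-only rule and the rule for unavailable post-intervention data. If it covers the 13, its description of the loss is wrong. If it covers only missing items, nothing in Section 2.4.3 addresses the loss of 13 women.

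**The text is a methods extract.** Participant flow, reasons and events usually belong in results, and consent material is not available here. This stands as a reason not to infer that the information was never collected. It does not excuse the sentence on bias, which is in the text and conflicts with a count in the same text.

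**48% overstates attrition.** A reader might take it as dropout from the classes, or as women stopping because of the intervention. The documents support neither. Eligibility was confirmed after consent, so some of the 13 may never have started, and a woman could also have finished the programme and missed the post-measures. The defensible figure is non-completion from consent, with loss among starters unknown between 0% and 48%.

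**Harms were ignored.** A reader might infer this from the missed-class call. The document does not support it. Section 2.4 describes staff inviting women to share their experience and raise concerns. Women unable to stand or too weak or ill were excluded, a certified leader assisted at classes, exertion was logged, and practice was self-paced and mild to moderate. What can be said is that no recorded question on harm or absence is described. Silence in this extract does not show that none was asked.

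**Conclusion.** The point holds for Section 2.4.3. Thirteen of 27 consented women (48%, exact 95% CI 29% to 68%) are absent from an analysis limited to completers without imputation. That is not a minor loss, and the expectation of no systematic bias cannot be checked from what is reported. Loss among starters falls within the planned 20% only if 10 or more of the 13 left before starting.

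This rests on two assumptions: that all 14 completers began the programme, and that the 27 and 14 count the same cohort. It does not claim that bias is present or which way it would run.

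The contacts in Section 2.3.4 are a secondary point for the next trial only. Conduct appears finished, so a new question cannot help this study. The home share of 60% to 75% measures exposure, not risk, and no serious harm is presumed.

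**What to change.** **Now, in Section 2.4.3.** Replace the sentence that expects no systematic bias with:

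> 13 of 27 consented women (48%) did not complete; analyses are in completers, and bias from this loss cannot be excluded.

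**Now, in the report.** From existing records, give the numbers consented, eligible, started and completed, the reasons for not starting or not completing, and any recorded adverse events. If a reason was not recorded, say so for that woman. Do not state that harms were not asked about unless the records confirm it. The cost is one changed sentence and one flow table.

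**Next trial only.** At each midweek contact, add a brief question on any fall, injury or new symptom. At each missed-class call, ask this and the reason for the absence. Record the dated answers. Where contact is by email, ask for a reply.

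No visit or procedure is added. At this study's size and 7 or 8 midweek contacts per woman (an assumption), and if every starter stayed, the question would be put between 14 × 7 = 98 and 27 × 8 = 216 times. Missed-class calls and the chasing of email replies would be extra. Contacts would run slightly longer and some unrelated complaints would be recorded.
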